8.2 Populations for Analysis

All efficacy and safety analyses will be conducted on the Intent-to-Treat population (ITT), defined as all randomized patients in the first period of study (first 6 weeks) who took at least one study treatment dose.

In addition to the primary analysis carried out on the ITT population, some secondary sensitivity analyses will be carried-out in accordance with the criteria mentioned above. The sensitivity analyses will be implemented according to the following criteria:

- Considering that a minimum intake of study treatment will be required for the assessment of the efficacy of therapy on the primary objective, it will be considered that evaluable patients on the primary end-point had taken at least 95% of the total dosage in the 6-week treatment period, as foreseen in the study protocol. Patients who will not reach this target will be excluded from the primary analysis, but entered in the sensitivity analysis to confirm the efficacy of treatment with Gerdoff® in the improvement of the high symptoms.
- Patients who took not allowed rescue medication will be excluded from the sensitivity analysis on the primary end-point.
- Patients who took drugs that interfere with salivary secretion remained included in the sensitivity
 analyses by derogation from the study protocol, since during the data review meeting the
 clinicians considered as not significant the interference of these drugs on the response of the
 primary variable.
- Patients who had a worsening of the upper symptoms and required an additional therapy or a modification of the dosage of omeprazole taken compared to the protocol during the 6-week

treatment period, according to the Investigator's opinion, will be considered major violators but remained in the study until visit V4 and entered into the ITT efficacy analysis. Such patients will be considered as non-responders in the analysis of the follow-up phase.

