6.4 Treatments

6.4.1 Identity of Investigational Device and Reference(s)

Investigational device:

Gerdoff® chewable tablets contain CS 400 mg, high molecular weight HA 10 mg and aluminium hydroxide 200 mg.

Details of the IMD are given in Section 5.1.

PPI (omeprazole)

Omeprazole will be the PPI available on the market and used during the study. Omeprazole will be taken as single agent or associated with Gerdoff® in the first 6 weeks of the study or as rescue medication (only if necessary) in the follow-up period, at constant dose and according to the Investigator's indication.

Route of administration: oral.

Dosage: two 20 mg capsules once daily in the morning before breakfast.

Packaging

The investigational products, Gerdoff® and omeprazole (PPI) will be provided free of change by Sofar S.p.A. by using batches available on the market.

The provided packages contained:

- Study period:
 - Packages of Gerdoff® for study period (Group 1)

At visit V1, each patient in Group 1 received 1 kit containing 14 marketed blisters of Gerdoff[®], each containing 10 tablets, to cover a treatment period of 6 weeks.

The patient took 3 tablets/day for 6 weeks (42 days), for a total of 126 tablets, which included 14 reserve tablets.

- Packages of omeprazole (PPI) for study period (Group 1 and 2)

At visit V1, each patient in Group 1 received 1 kit containing 14 marketed blisters of omeprazole, each containing 7 capsules, to cover a treatment period of 6 weeks.

The patient took 2 capsules/day, in the morning before breakfast, for 6 weeks (42 days), for a total of 84 capsules, which included 14 reserve capsules.

- Follow-up period:
 - Packages of Gerdoff[®] for follow-up period

At visit V4, each patient included in the follow-up period and randomised in the treatment group received 2 kits of investigational product. Each kit contained 14 marketed blisters of Gerdoff[®], each containing 10 tablets, to cover a treatment period of 6 weeks.

The patient took 3 tablets/day for 6 weeks (42 days), for a total of 126 tablets, which included 14 reserve tablets.

- Packages of omeprazole (PPI) as rescue medication for the follow-up period

At visit V4, each patient included in the follow-up period received 2 kits containing the rescue medication scheduled for the study. Each kit contained 14 marketed blisters of omeprazole, each containing 7 capsules, to cover a treatment period of 6 weeks, including 14 reserve capsules.

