6.4.2 Treatment Administered

Eligible patients will be randomly assigned to one of the two following treatment groups:

Treatment period

- Group !
 - Gerdoff®: CS, HA and aluminium hydroxide chewable tablets.

Route of administration: oral

Dosage regimen: one tablet three times daily: 1 tablet after breakfast, 1 tablet after lunch and 1 tablet in the evening before retiring to bed.

Treatment duration: 6 weeks \pm 2 days.

- Omeprazole (proton pump inhibitor, PPI)

Route of administration: oral.

Dosage: two 20 mg capsules once daily in the morning before breakfast.

• Group 2

- Omeprazole (proton pump inhibitor, PPI)

Route of administration: oral.

Dosage: two 20 mg capsules once daily in the morning before breakfast.

Treatment duration: 6 weeks \pm 2 days.

Follow-up period

During the 12-week follow-up period, which started from the end of study visit V4, responder patients of Group 1 will be randomly assigned to receive treatment with Gerdoff®, according to the above reported dosage, or will be assigned to the control group and will be therefore not treated. All patients received a packaging of omeprazole, to be taken only if necessary, at constant dose and according to the indications of the Investigator.

The scheduled duration of the follow-up period will be 12 weeks \pm 3 days for both treatment groups.

Administration of investigational products

• Study period

Patients will be instructed to take, starting from the morning of the day following Visit V1, the investigational products every day for the next 6 weeks.

• Follow-up period

Patients will be instructed to take, starting from the morning of the day following Visit V4, the investigational products every day for the next 12 weeks.

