6.4.5 Compliance and Device Accountability

Patients will be instructed to record in the daily diary the amount of investigational products taken during the entire study period, highlighting that the administered quantity will be not to be lower than that scheduled for the study to not invalidate the efficacy of treatment.

At the end of the study, the Investigator counted the amount of tablets and of capsules returned by the patient and compared this amount with the quantities reported in the patient daily diary. In case of discrepancies, clarifications will be asked to the patient and will be reported in the clinical records/worksheet and in the eCRF.

The study monitor counted the returned investigational products and compared the returned quantity with the use reported in the patient diary to assess the patient's adherence to the scheduled dosage.

Patients with values of compliance $\geq 95\%$ of the overall dosage scheduled in the 6-week treatment period, evaluated on the basis of minimal taken daily dose, will be considered as adherent to treatment

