6.5 Study Procedures and Study Schedule

6.5.1 Overview of Data Collection

The study plan and scheduled examination and procedures are summarised in the following flow-chart (Figure 2).

Figure 2. Flow-chart of the study

Visit	V1 Baseline	V2 (intermediate visit)	V3 (intermediate visit)	V4 ^(a) End of study/ Early interruption ^(c)	V5 ^(b) Follow-up (control visit) ^(d)	interruption ^(c)
Period	Т0	T 1 1 week ± 1 day	T 3 3 weeks ± 2 days	T6 6 weeks ± 2 days	T12 12 weeks ± 3 days	T18 18 weeks ± 3 days
Informed consent	X		•	-	Ĭ	•
Inclusion/exclusion criteria	X					
Demographic data	X					
Vital signs	X			X		X
First GERD diagnosis or diagnosis confirmation	X					
Anamnesis	X					
Reference. ENT specialist	X					
Objective examination and concomitant diseases	X			X		X
Assessment of symptoms	X	X	X	X	X	X
Haematology and blood chemistry	X			X		X
Beta-hCG (1)	X			X		X
Treatment dispensing Gerdoff® + PPI or PPI	X					
Treatment dispensing Gerdoff®/no treatment and rescue (2)				X		
Concomitant therapies	X	X	X	X	X	X
Likert scale	X	X	X	X	X	X
RSI questionnaire	X	X	X	X	X	X
Diary dispensing/returning	X	X	X	X	X	X
Questionnaire of treatment likelihood		X	X	X		
Assessment of responder/ non-responder patients				X		
Assessment of maintenance of the effect						X
Incidents/adverse events		X	X	X	X	X

Visit	V1 Baseline	V2 (intermediate visit)	V3 (intermediate visit)	V4 ^(a) End of study/ Early interruption ^(c)	V5 ^(b) Follow-up (control visit) ^(d)	V6 ^(b) End of follow- up/Early interruption ^(c)
Period	Т0	T 1 1 week ± 1 day	T 3 3 weeks ± 2 days	T6 6 weeks ± 2 days	T12 12 weeks ± 3 days	T18 18 weeks ± 3 days
Assessment of compliance to Gerdoff® and PPI, and product accountability				X		
Assessment of compliance to Gerdoff® and product accountability						X
Use of rescue medication (3)		X	X	X	X	X
End of study visit				X		
End of follow-up visit						X

- (a) End of study visit for all patients included in the study. Responder patients included in Group 1 (Gerdoff®+PPI) immediately continued the study with the follow-up phase.
- (b) Only responder patients included in Group 1 (Gerdoff®+PPI) will be included in the follow-up phase.
- (1) Only in childbearing potential women.
- ⁽²⁾ Only in responder patients in Group 1 that took part in the follow-up study.

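### Section 8.2 bases the primary analysis on ITT yet excludes patients below 95% of dosage from it, and the compliance denominator behind that exclusion is undefined and can treat the arms differently

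*Combined protocol and SAP*

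**What the plan says.** Section 8.2 opens by placing all efficacy and safety analyses on ITT, defined as patients randomised in the first period who took at least one dose, and then calls the ITT analysis the primary one. The first bullet of its sensitivity criteria says that "evaluable patients on the primary end-point had taken at least 95% of the total dosage in the 6-week treatment period". It adds that patients below that level leave the primary analysis and enter the sensitivity analysis.

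The cut comes from section 6.4.5, which counts as adherent a patient with at least 95% "of the overall dosage scheduled in the 6-week treatment period, evaluated on the basis of minimal taken daily dose". It gives no formula and does not explain the closing clause.

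Other passages that bear on the calculation:
- Section 6.4.1, tablets: "The patient took 3 tablets/day for 6 weeks (42 days), for a total of 126 tablets, which included 14 reserve tablets". For omeprazole it gives two capsules a day "for 6 weeks (42 days), for a total of 84 capsules", also said to include 14 reserve units.
- Section 6.4.2: dosing begins "starting from the morning of the day following Visit V1". Omeprazole is taken entirely in the morning; the third Gerdoff tablet is taken at bedtime. Treatment duration is itself given as 6 weeks ± 2 days.
- Section 6.5.1, Figure 2: V4 is at "T6 6 weeks ± 2 days", and compliance with both products is assessed there.
- Section 6.5.2, Visit 4: remaining product is collected and counted.

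**The concern.** Section 8.2 supports two different primary populations. One keeps every treated patient. The other drops patients on the basis of what happened after randomisation, in an open-label trial planned with 39 per arm. A programmer could implement either and cite the text.

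The exclusion is also not neutral between arms. Group 2 is measured on a once-daily morning dose. Group 1 also has a product whose last daily dose falls after a daytime visit. If the count is set against a fixed 42-day total, an early V4 costs Group 1 more than Group 2, and a patient can be dropped because of the visit date and not because of missed doses. At stake are the comparability of the arms in the primary comparison and a primary set that is not uniquely defined.

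**Working it through.** **Inputs.** Three tablets and two capsules a day; 42 days (6.4.1). First dose the day after V1 (6.4.2), so a V4 on day *d* is the *d*-th dosing day. V4 on days 40 to 44 (Figure 2). Cut 95% (6.4.5, 8.2).

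**Plan's own totals.** 3 × 42 = 126 and 2 × 42 = 84; both reproduce.

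**Cut with fixed totals.** 0.95 × 126 = 119.7, so 120 tablets are needed. 0.95 × 84 = 79.8, so 80 capsules are needed.

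**No missed dose, V4 on day 40.** Doses possible = daily dose × 39 + doses taken on day 40 before product is returned.

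| Product returned | Tablets / 126 | Capsules / 84 | Pooled / 210 |
|---|---|---|---|
| Before any dose | 117 = 92.9%, fail | 78 = 92.9%, fail | 195 = 92.9%, fail |
| After breakfast | 118 = 93.7%, fail | 80 = 95.2%, pass | 198 = 94.3%, fail |
| After lunch | 119 = 94.4%, fail | 80 = 95.2%, pass | 199 = 94.8%, fail |
| After bedtime tablet | 120 = 95.2%, pass | 80 = 95.2%, pass | 200 = 95.2%, pass |

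The arms therefore separate only when product is returned after the morning capsules and before the bedtime tablet, and only if Group 1 is judged on tablets or on the pooled count.

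**Days 41 to 44.** The lowest possible full-adherence score is on day 41 before any dose: 120/126 = 80/84 = 95.2%. Every fully adherent patient passes in both groups.

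**Denominator matched to actual days.** Day 40, whole days: tablets 118/120 = 98.3% or 119/120 = 99.2%; capsules 80/80 = 100%. Counting only doses due by the time of the visit gives 118/118 and 80/80. Both groups pass.

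**How many patients.** The documents give no V4 dates, so this is a range under assumed distributions, with perfect adherence, a fixed denominator and a V4 after the morning doses but before bedtime:
- 5% of visits on day 40: 5% of Group 1 fails (0.05 × 39 ≈ 2 patients), 0% of Group 2.
- Visits uniform over days 40 to 44: 20% of Group 1 fails (0.20 × 39 ≈ 8 patients), 0% of Group 2.

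**Imperfect adherence.** The margin is also narrower for tablets on day 41. After breakfast 121 are possible against 120 needed, so one may be missed; for capsules 82 against 80, so a full day's dose may be missed. As an illustration, take 99% of doses independently taken, the two capsules as one dosing event, a V4 after breakfast, and both products required in Group 1. Then 28% of Group 1 and 8% of Group 2 fail with uniform visit days. With 70% of visits on day 42, 10% each on days 41 and 43 and 5% each on days 40 and 44, it is 10% and 3%. With a matched denominator it is about 1% in each arm.

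**Kit counts.** 14 × 10 = 140 tablets and 14 × 7 = 98 capsules are dispensed, which exceed 126 and 84 by 14 each. Section 6.4.1 instead says that 126 and 84 include the 14, which would leave 112 and 70.

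**The case against.** Nothing in the documents names 126 or 84 as the compliance denominator; they come from the packaging text. Section 6.4.2 attaches the ±2-day window to treatment duration itself, so a denominator based on each patient's own days is equally available, and under it the day-40 problem disappears. The undefined reference in section 6.4.5 to a minimal daily dose may point to a per-day basis. Taken literally, the reserve wording gives 112 and 70 scheduled units, and both day-40 patients pass. Section 8 also refers to a final SAP in Annex 10, whose text is not in the material reviewed and may settle the derivation. All of this stands.

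A reader might infer that the plan does use a fixed 42-day total, that Group 1 must pass on each product separately, or that 20% of Group 1 will be lost. The documents state neither of the first two, and the third rests on an assumed uniform spread of visits. Nor does 42 against 40 days alone separate the arms: 40 complete days give 95.2% for both products. The gap comes from the part-day of tablets at the visit.

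It can also be said that the 95% bullet sits among sensitivity criteria, so ITT governs and the primary result is untouched. That is a reasonable reading of intent, but the bullet says in terms that these patients leave the primary analysis. The conflict remains until the text is changed.

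**Conclusion.** The firm finding is the contradiction in section 8.2: an ITT primary analysis and a 95% compliance exclusion from it. No assumption is needed for that.

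The arm difference is conditional. It needs the exclusion to be applied, a fixed 126/84 denominator, product returned between the morning capsules and the bedtime tablet, and Group 1 judged on tablets or a pooled count. For fully adherent patients it then arises on one of the five permitted visit days, with 93.7% or 94.4% against 95.2%. The share of Group 1 affected is about 5% to 20% under the two visit distributions shown, against 0% of Group 2; the true share cannot be derived from the documents. The missing denominator and the missing rule for combining products are gaps on any reading, because different defensible choices yield different evaluable sets. The change should be made before analysis.

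**What to change.** - **Section 8.2:** delete the exclusion of patients below 95% from the primary analysis, keep ITT as the primary population, and use the 95% cut only to define a per-protocol sensitivity set.
- **Sections 6.4.5 and 8.2:** define compliance for each product as doses taken divided by doses scheduled from the first dose to the actual V4 date and time. State how the two products are combined in Group 1, and define or remove the minimal-daily-dose clause.
- **Section 6.4.1:** reconcile the counts (140 and 98 dispensed, against 126 and 84 said to include 14 reserve units), so that dispensed and scheduled quantities cannot be confused.

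The cost is wording and one derivation rule. Visit dates, diary entries and returned counts are already collected; the time of product return can be taken as the visit time or, if that is not recorded, fixed by a stated convention. Sample size and visits do not change.

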8 STATISTICAL METHODS

The statistical methods will be planned in the protocol and will be then updated, agreed and approved in the final Statistical Analysis Plan (SAP), version 1.1, dated 19 February 2019 (Annex 10).

Statistical analysis will be performed by the statistical department of High Research S.r.l., [name].

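### Section 8.2 contradicts itself on the primary analysis set: two sentences make it ITT, but the first bullet excludes patients below 95% of the dosage

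*Combined protocol and SAP*

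**What the plan says.** Section 8.2 opens with a general rule: "All efficacy and safety analyses will be conducted on the Intent-to-Treat population (ITT"), and defines that set as patients randomised in the first period who took at least one dose. The next paragraph repeats the choice: "In addition to the primary analysis carried out on the ITT population, some secondary sensitivity analyses will be carried-out". Four bullets follow, introduced as criteria for the sensitivity analyses.

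The first bullet argues that a minimum intake is needed to judge efficacy on the primary objective. It treats patients as evaluable for the primary endpoint if they took at least 95% of the 6-week dosage, and adds: "Patients who will not reach this target will be excluded from the primary analysis, but entered in the sensitivity analysis". The fourth bullet deals with patients who worsened and needed additional therapy or a changed omeprazole dosage. They "will be considered major violators but remained in the study until visit V4 and entered into the ITT efficacy analysis".

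Section 8.3.1 specifies a Student's t-test on the RSI change at 6 weeks and names no population. Section 6.4.5 uses the 95% threshold, "evaluated on the basis of minimal taken daily dose, will be considered as adherent to treatment", and attaches no exclusion to it. Section 8 points to a separate final SAP, version 1.1 (Annex 10), which is not among the documents supplied.

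**The concern.** The trial has one primary comparison, and its analysis set should have one definition. Two analysts could each follow section 8.2 faithfully and test different patients. In an open-label trial the choice between the two sets could also be made, or be suspected of having been made, with knowledge of treatment.

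The two sets differ in kind. ITT compares the groups as randomised (apart from patients who never took a dose). The 95% set selects patients on behaviour after randomisation. Treatment is known to the patient (sections 6.1 and 6.4.8), and the RSI is completed by the patient (section 6.5.2). Group 1 takes two products and Group 2 takes one (section 6.4.2), so equal exclusion in the two arms cannot be presumed.

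**Working it through.** **1. The plan's own figure.** Section 8.1 gives a difference of 3.6, SD 5, two-sided 5% and 80% power. The normal formula gives n per arm = 2 × [5 × (1.960 + 0.842) / 3.6]² = 30.28, rounded up to 31 (62 in all). With 20% drop-out, 31 / 0.80 = 38.75, so 39 per arm (78 in all). Both figures reproduce. The contradiction does not affect them.

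**2. One patient traced through section 8.2.** Take a randomised patient with 114 of 126 tablets (90.5%).

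| Text | In the primary analysis? |
|---|---|
| General rule: ITT, at least one dose | Yes |
| Second paragraph: primary analysis on ITT | Yes |
| Bullet 1: below 95% | No; sensitivity analysis only |
| Bullets 2 to 4 | Do not address compliance; compatible with ITT |
| Section 8.3.1 | Silent |
| Section 6.4.5 | Not adherent; no exclusion stated |

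Read literally, bullet 1 makes the primary set the compliant subset and brings the less compliant patients in only for the sensitivity analysis. That reverses the second paragraph.

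**3. How tight the cut is.** Section 6.4.1 schedules 126 tablets and 84 capsules over 42 days.
- Tablets: 0.95 × 126 = 119.7, so 120 are needed and at most 6 may be missed.
- Capsules: 0.95 × 84 = 79.8, so 80 are needed and at most 4 may be missed.
- Full days: 40/42 = 95.2% passes; 39/42 = 92.9% fails.

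The exact count also depends on how the reference in section 6.4.5 to the minimal daily dose is read, and on whether the denominator stays at 42 days when V4 falls 2 days early or late.

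**4. Bias if bullet 1 were followed.** In one arm, let p be the share excluded and D the mean RSI improvement of retained patients minus that of excluded patients. The retained mean exceeds the full-arm mean by p × D. The bias in the between-arm difference is therefore p₁D₁ − p₂D₂. The documents give none of these four quantities. Assumed values show that the sign is open:
- 20% excluded in each arm, gaps 5 and 2.5: 0.20 × 5 − 0.20 × 2.5 = +0.5 points.
- The same gaps with the arms reversed: 0.20 × 2.5 − 0.20 × 5 = −0.5 points.
- 20% with gap 2.5 against 10% with gap 5: 0.20 × 2.5 − 0.10 × 5 = 0.

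**5. Power if bullet 1 were followed.** Noncentral t, difference 3.6, SD 5, standard error 5 × √(1/n₁ + 1/n₂). The exclusion share of about 20% is an assumption.
- Planned evaluable number, 31 v 31: SE 1.270, power 79.6%.
- About 20% excluded in one arm, on top of the planned drop-out, 25 v 31: SE 1.344, power 74.9%.
- About 20% excluded in one arm, taken from the 39 randomised with no other loss, 31 v 39: SE 1.203, power 83.9%.

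Power falls below or stays above the planned 80% depending on whether exclusions add to drop-out, which the documents do not say.

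**The case against.** The strongest reply is that this is a drafting slip. The general rule and its repetition both say ITT. Bullet 1 stands in a list of sensitivity criteria, and bullet 4 keeps even major violators in the ITT efficacy analysis. Exchanging *primary* and *sensitivity* in one clause would restore the usual layout. Because the general rule covers every efficacy analysis, section 8.3.1 had no strict need to name a set. Even the reference to evaluability on the primary endpoint could mean evaluability for a sensitivity analysis of that endpoint, since bullet 2 speaks of such an analysis.

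Much of this stands: ITT is the better-supported reading. But the slip is not proven. Bullet 1 gives a reason for requiring a minimum intake, ties evaluability on the primary endpoint to 95%, states the exclusion, and says what the sensitivity analysis of the excluded patients is for. That is a worked-out rule and not one stray word.

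A second reply is that SAP version 1.1 may already settle the point. That cannot be checked here, so the finding concerns the supplied text only.

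A reader might infer more: that the primary result will rest on compliant patients, that the estimate is tilted towards Gerdoff, or that the trial loses power. The documents support none of these. They do not show which rule is applied, and they give no adherence data. Steps 4 and 5 show that the sign of the bias and the effect on power both turn on assumed values.

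**Conclusion.** The contradiction is real and is in the current text. As written, bullet 1 is wrong: if followed, it would condition the only primary test on adherence after randomisation, against two statements that the test is on ITT. It should be corrected before analysis.

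No figure can be put on the consequence. What the documents do show is that the threshold is strict enough to matter: three fully missed days out of 42 put a patient below it. Confidence is high for the wording supplied, and does not extend to the content of Annex 10 or to how the data are in fact analysed.

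**What to change.** - In sections 8.2 and 8.3.1, state that the primary t-test uses the ITT set as already defined, analysed as randomised and regardless of compliance.
- Replace the whole last sentence of bullet 1. The new sentence should say that patients below 95% of the dosage stay in the primary ITT analysis and are left out of the supportive (per-protocol) sensitivity analysis. Deleting only the exclusion is not enough, because the remaining clause would still place these patients in the sensitivity analysis.
- Leave bullet 2 as it is. It already assigns the exclusion for non-permitted rescue to the sensitivity analysis and does not conflict with ITT.
- Check that SAP version 1.1 (Annex 10) says the same.
- Bullet 3 reports a decision taken at the data review meeting. If that meeting has already been held, date the change and record its justification.

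The cost is wording, plus that dated record where it applies. No new data, visits or patients are needed. Compared with an analysis that followed bullet 1, the result could move in either direction.

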1.3 Investigation Rationale

The aim of the present study will be to evaluate, in first diagnosed patients presenting with upper symptoms associated with GERD, the effect of a 6-week treatment with a combination based on CS, HA and aluminium hydroxide (Gerdoff®), co-administered with a treatment with PPIs, compared to treatment with PPIs as monotherapy, i.e. to verify, in patients treated with the combination of the two products, the reduction in symptoms frequency by means of a Likert questionnaire and the severity of upper symptoms by means of the Reflux Symptom Index (RSI) questionnaire (13), and to collect safety data. After 6 weeks of treatment, patients included in the two groups will be then classified as responders or non-responders. Responder patients will be defined as those patients that, at the 6th week of treatment, reached a RSI score decreased for at least 50% compared to baseline and an absolute value < 13.

Furthermore, the maintenance of the effect of treatment on the extra-oesophageal symptoms will be evaluated after a period of follow-up lasting 12 weeks, which could be entered only by responder patients randomised in the Gerdoff®-PPI arm. Patients included in the follow-up period will be randomised to receive Gerdoff® or no treatment (control group). Safety data will be also evaluated in the group of patients that continued in the follow-up period.

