8.3.2 Secondary Performance Analyses

All secondary variables will be listed and presented with the most appropriate descriptive statistics.

Number and percentage of responder/non-responder patients at end of treatment (visit V4)

Patients who at the 6th week of treatment showed a reduction of at least 50% vs. the baseline and an

absolute value < 13 will be considered as responders. The Chi-square test with the correction of Yates or, if more appropriate, the Exact Fisher's test will be used to compare the distribution of the proportions of responders and non-responders in the two treatment groups. The patients responders in the group treated with Gerdoff® + PPI entered the follow-up period and continued in the observation according to the procedures provided by the study protocol;

Change of frequency of symptoms from baseline to end of treatment (visit V4) of frequency of symptoms, assessed using the Likert scale

The same analyses foreseen for the RSI questionnaire will be performed.

Use of rescue medication

In the first 6 weeks of treatment, the intake in each treatment group of the rescue medication, allowed or not allowed, will be calculated as the frequency of intake of the specific drug and the comparison between groups will be performed using the Fisher's exact test.

In the first 6 weeks of treatment, the comparison of the median dose of rescue medication in the two study groups will be performed by means of the non-parametric (distribution-free) test of the median. If a mean value of intake could also be calculated, the comparison between the two treatment groups will be performed using the Mann-Whitney U test.

Patient satisfaction of treatment

This evaluation will be expressed with a semi-quantitative ordinal scale: 0 = low, 1 = discrete, 2 = good, 3 = excellent). The frequencies of judgments will be compared between groups using the Chisquare Mantel-Haenszel test.

In the follow-up period, the efficacy data collected will be presented by treatment group using only the most appropriate descriptive statistics and consistent with the current numerosity of the sample.

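### Patients who need added GERD therapy before V4 are labelled non-responders only in the follow-up analysis, so the between-arm responder test at V4 can count responses obtained with that therapy

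*Combined protocol and SAP*

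**What the plan says.** - **Added therapy before V4 (section 8.2).** Patients who worsened and, in the investigator's opinion, needed additional therapy or a changed omeprazole dosage in the first six weeks "will be considered major violators but remained in the study until visit V4 and entered into the ITT efficacy analysis". The next sentence reads: "Such patients will be considered as non-responders in the analysis of the follow-up phase".
- **Responder rule (sections 1.3 and 8.3.2).** Section 1.3 defines a responder as a patient who at week 6 "reached a RSI score decreased for at least 50% compared to baseline and an absolute value < 13". Section 8.3.2 repeats the rule: after the 50% reduction, patients with an "absolute value < 13 will be considered as responders". Neither section sets a condition on added therapy.
- **Between-arm test (section 8.3.2).** A Yates-corrected chi-square or Fisher's exact test "will be used to compare the distribution of the proportions of responders and non-responders in the two treatment groups". The V4 responder proportion is listed first among the secondary objectives in section 2.2.
- **Follow-up (section 6.5.1, Figure 2 note (b), and section 8.3.2).** "Only responder patients included in Group 1 (Gerdoff®+PPI) will be included in the follow-up phase". Efficacy data from this period are presented "using only the most appropriate descriptive statistics and consistent with the current numerosity of the sample".
- **Withdrawal and retention (sections 6.3.3 and 6.4.6).** Section 6.3.3 lists intake of other GERD therapy among the events that require discontinuation, and treats early discontinuation as treatment failure. Section 6.4.6 leaves it to the investigator whether a patient who took a non-permitted medication stays in the study.

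**The concern.** The non-responder label is attached to a phase with no Group 2 patients and no hypothesis test. It is not attached to V4, the one place where responder proportions are tested between arms. There, a patient kept in the study is classified by the RSI alone, whatever else was taken to bring it down.

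Two patients with the same event can also be classified differently. One who is withdrawn is a treatment failure, and one who is retained may be a responder. Which applies depends on a decision by an investigator who knows the allocation, because the trial is open-label (section 6.4.8).

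At stake is the first secondary comparison. If PPI-alone patients receive more added therapy, their assisted responses shrink the difference between arms. If Gerdoff-PPI patients receive more, the difference grows.

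**Working it through.** **Reading the sections together**

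1. Section 8.2 places the retained patients in the ITT efficacy analysis.
2. Sections 1.3 and 8.3.2 classify ITT patients at V4 by the RSI alone.
3. The only sentence that would override step 2 is confined to the follow-up analysis.
4. The sensitivity analysis in section 8.2 that excludes users of non-allowed rescue medication is limited to the primary endpoint, the RSI change. The responder comparison has no counterpart.
5. The failure rule in section 6.3.3 reaches only patients who discontinue early.

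For patients retained to V4, nothing therefore sets an assisted response to non-response in the V4 test.

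**The plan's own figure**

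Section 8.1 sizes the trial on RSI change: delta 3.6, SD 5, two-sided 5%, power 80%.

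n per arm = 2 × (1.960 + 0.842)² × 5² / 3.6² = 2 × 7.849 × 25 / 12.96 = 30.3, rounded up to 31, so 62 in total.

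With 20% drop-out: 62 / 0.80 = 77.5, rounded up to 78, or 39 per arm.

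Both figures reproduce and are unaffected by this point. The plan states no power for the responder endpoint.

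**Illustration**

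The following are assumptions, not taken from the documents:

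- all 39 patients per arm are classified at V4;
- 65% of Group 1 and 35% of Group 2 respond without added therapy;
- a share *s* of each arm receives added therapy, and a fraction *c* of those patients meets the RSI rule.

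Rate under the RSI-only rule = unassisted rate + *s* × *c*. For example, with *s* = 5% v 15% and *c* = 50%: 65 + 5 × 0.5 = 67.5% and 35 + 15 × 0.5 = 42.5%.

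Power is from exact binomial enumeration of the Yates-corrected chi-square at two-sided 5%.

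| Added therapy, Group 1 v 2 | *c* | Responders, RSI-only | Difference (points) | Power |
|---|---|---|---|---|
| Assisted responses not counted | – | 65% v 35% | 30 | 70% |
| 5% v 15% | 10% | 65.5% v 36.5% | 29 | 67% |
| 5% v 15% | 20% | 66% v 38% | 28 | 64% (63.5%) |
| 5% v 15% | 50% | 67.5% v 42.5% | 25 | 53% |
| 15% v 5% | 50% | 72.5% v 37.5% | 35 | 84% |
| 10% v 10% | 50% | 70% v 40% | 30 | 70% |

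**How few patients matter**

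Suppose 22 of 39 v 14 of 39 are responders by the RSI alone: difference 8/39 = 20.5 points, Yates p = 0.112.

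- If 1 v 4 of them had added therapy and are set to non-response: 21 v 10, difference 11/39 = 28.2 points, p = 0.021.
- If 4 v 1: 18 v 13, difference 5/39 = 12.8 points, p = 0.355.
- If 2 v 2: 20 v 12, difference still 20.5 points, p = 0.107.

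**The case against.** The case on the other side has five parts.

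- **Section 8.2 need not contradict note (b).** A reader might infer that labelling patients non-responders in a phase that admits only responders is a contradiction. The documents do not force that. The sentence can be read as a bar on follow-up entry, which agrees with note (b) and gives the label a function. This objection stands: the wording is ambiguous. Even on that reading the V4 test is unchanged, and a Group 1 patient could be a responder in the test and a non-responder for follow-up.
- **Withdrawn patients are already failures.** This also stands, and it narrows the gap to patients retained to V4. It also exposes the unequal treatment of the same event.
- **Using outcomes regardless of added therapy is a recognised strategy.** Section 8.2 does choose ITT inclusion, and sections 8.3 and 8.3.2 tabulate rescue use and compare it between arms, so an imbalance would be visible. That is fair, but the plan does not present RSI-only classification as a deliberate strategy for this endpoint. It also treats these patients as non-responders elsewhere, and seeing an imbalance does not show its effect on the responder result.
- **The size is assumed.** Patients who worsened may seldom reach a 50% fall and an RSI below 13, so 50% conversion may be high. At 10% conversion the loss is about three points of power. This stands.
- **A later SAP may settle it.** Section 8 refers to a final SAP, version 1.1, in Annex 10. If that is a separate document, it could not be checked here.

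**Conclusion.** The concern holds for patients retained to V4. That an assisted response counts in the between-arm test is an inference from the RSI-only rule and ITT inclusion. No sentence says so outright, but none in these documents prevents it.

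Under the stated assumptions, with added therapy in 5% v 15%, power falls from 70% to between 67% and 53% as conversion rises from 10% to 50%. With use reversed and 50% conversion, the difference is inflated from 30 to 35 points. Equal use changes nothing.

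A reader might infer that the rule favours Gerdoff. The documents do not support that, because the direction depends on which arm receives more added therapy and they give no rates. Nor is this a loss of planned power, since the trial is powered on RSI change only. The point concerns a tested secondary endpoint and should be corrected.

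**What to change.** **Change to sections 8.2 and 8.3.2.** State that, for the V4 responder analysis in both arms, patients who received additional GERD therapy or a modified omeprazole dosage between V1 and V4 are counted as non-responders, in line with the failure rule for withdrawn patients. Report the RSI-only classification as a sensitivity analysis.

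**Reconcile.** Sections 6.3.3, 6.4.6, 6.5.1 (Figure 2 note (b)) and 8.2 must be aligned on whether such patients are retained and whether Group 1 patients among them enter follow-up. No clinical rule is proposed. Until that is settled, the analysis label should be kept distinct from the classification that decides follow-up entry.

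**Cost.** One sentence and one sensitivity row, using data on therapies and rescue use already collected at V2 to V4, with no change to sample size or visits. Reported responder rates will be slightly lower. The main result will also depend on an open-label decision to add therapy, which is itself a possible source of bias. The RSI-only row shows how far the result rests on it.
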